**Table 2. Outcome Measurements: Readmissions and Associated LOS and Cost/Charges**

Variable	Role	Operational definition
MB-related Readmission	Outcome	
Defined as readmissions with a bleeding diagnosis at the first position of the hospital discharge diagnosis codes.
 
Number and percentage of patients with MB-related readmissions within 1 or 3 months of initial NVAF hospitalization in study cohorts will be reported. Associated LOS and cost for MB-related readmissions will be determined. Likelihood of first MB-related readmission was assessed for each OAC cohort vs. the apixaban cohort. LOS and hospital cost per patient for cohorts will be estimated and compared by multivariable regression analysis. Measurements for 3-month readmissions will be evaluated using descriptive statistics as an exploratory analysis.

All-cause Readmission	Outcome	
Number and percentage of patients with all-cause readmissions within 1 or 3 months of initial NVAF hospitalization in study cohorts will be reported. Associated LOS and cost for all-cause readmissions will be determined. Likelihood of first all-cause readmission was assessed for each OAC cohort vs. the apixaban cohort. LOS and hospital cost per patient for cohorts will be estimated and compared by multivariable regression analysis. Measurements for 3-month readmissions will be evaluated using descriptive statistics as an exploratory analysis.

Stroke-related Readmission	Outcome	
Defined as readmissions with a stroke diagnosis at the first position of the hospital discharge diagnosis codes. Cases will be excluded if traumatic brain injury (ICD-9: 800-804, 850-854) was present during hospitalization.
 
Number and percentage of patients with stroke-related readmissions within 1 or 3 months of initial NVAF hospitalization in study cohorts will be reported. Associated LOS and cost for stroke-related readmissions will be determined. Measurements for stroke-related readmissions will be evaluated using descriptive statistics as an exploratory analysis.

#### 8.4. Data sources

The data source is the Premier Hospital database, which provides hospital billing information on a patient’s hospital stay as well as information on ICD-9 and ICD-10 codes and current procedural terminology codes. Specifically, the database contains a date-stamped log of all billed items, including medications, laboratory, diagnostic, and therapeutic services, and primary and secondary diagnoses for each patient’s hospitalization. Identifier-linked files provide demographic and payer information. Detailed service-level information for each

hospital day is recorded and this includes details on medication received. Billed items are standardized by the database vendor after the hospital both reviews and consents to the items.

### 8.5. Study size

The preliminary data evaluation of the Premier database indicated that there are at least 30,000 patients for each of OAC cohort during the study period described for this study. With a two-sided test, an alpha-level of 0.05, and a 1:1 ratio of the comparison cohorts, and the assumed one-month MB-related readmission rate of 1.4%, and the assumed MB-related readmission rate difference of 0.5% between cohorts treated with other OACs vs. apixaban, we have estimated the following power calculation.

**Table 3. Power Calculation**

Power Calculation		
Nominal Power	Actual Power	N Total-One Arm
0.7	0.7	11,226
0.75	0.75	12,622
0.8	0.8	14,274
0.85	0.85	16,328
0.9	0.9	19,108
0.95	0.95	23,630

Thus, the study is expected to have sufficient sample sizes for the study measurements.

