recent patient data from 2007 to 2008), little information exists in the published literature on bleeding-related readmissions. In the real-world setting bleeding is a significant burden healthwise and economic wise and represents a critical target for improving the quality of care of NVAF patients. In clinical trials NVAF patients treated with the different DOACs differed in bleeding rates and the DOACs with lower bleeding risk have potentially a greater likelihood of improving the anticoagulation management of NVAF patients in the real-world setting where bleeding rates are higher than observed in the clinical trial setting. We previously conducted an early evaluation that investigated rates of all-cause and bleeding-related hospital readmissions among NVAF patients treated with dabigatran, rivaroxaban, and apixaban (January 1, 2012 through March 31, 2014). In this early analysis of 74,730 patients identified from the Premier Hospital database, after controlling for differences in patient characteristics, compared with patients who received apixaban during their index hospitalizations, the odds of bleeding-related hospital readmissions were significantly greater by 1.4-fold ( $p < 0.01$ ) for patients who received rivaroxaban and 1.2-fold ( $p = 0.16$ ) numerically trending greater for patients who received dabigatran. This current analysis will be a follow-up of our earlier assessment and will include patients treated with warfarin in addition to NVAF patients treated with DOACs. Recent real-world evidence has suggested that unmeasured or unmeasurable secular trends in prescribing patterns may contribute to differential outcomes observed with DOACs. For this study, patients hospitalized for NVAF and treated with OACs will be identified from January 1, 2013 through June 30, 2017, a time period in which dabigatran, rivaroxaban, and apixaban were all available, and 1- and 3-month readmission outcomes will be evaluated.

This non-interventional study is designated as a Post-Authorisation Safety Study (PASS) and is conducted voluntarily by Pfizer.

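### Table 3 labels both-arm totals as one-arm sizes, overstating the per-arm requirement twofold, and section 8.5 does not say which cohort has the 1.4% rate

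*Protocol*

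**What the plan says.** Section 8.5 sets the test as follows: "With a two-sided test, an alpha-level of 0.05, and a 1:1 ratio of the comparison cohorts". It adds "the assumed one-month MB-related readmission rate of 1.4" per cent and "the assumed MB-related readmission rate difference of 0.5% between cohorts treated with other OACs vs. apixaban". It does not say whether 1.4% belongs to apixaban or to the comparators, or which of the two is assumed to be higher.

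Table 3 then gives 11,226 / 12,622 / 14,274 / 16,328 / 19,108 / 23,630 for power 0.70 / 0.75 / 0.80 / 0.85 / 0.90 / 0.95, in a column headed "N Total-One Arm". The abstract carries the same table.

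On available data, section 8.5 reports that "there are at least 30,000 patients for each of OAC cohort during the study period". It concludes: "Thus, the study is expected to have sufficient sample sizes for the study measurements".

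Section 8.7 says that the loss of patients in propensity score matching is unknown. If too few remain, it replaces the matched comparison with a multivariable logistic regression. It gives no number for too few.

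**The concern.** The column heading contains both the word for a total and the words for one arm, and a reader planning matched cohorts will take it as a per-arm size. If the figures are really totals, every per-arm requirement is stated at twice its value.

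The missing cohort and direction compound this. At rates near 1%, the variance depends strongly on the level of the rates, so 1.4% against 0.9% and 1.4% against 1.9% need clearly different sizes for the same 0.5-point gap. A reader cannot tell from the text which was powered.

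What is at stake is the decision after matching. Table 3 holds the only sample sizes tied to power in the protocol. Someone asking whether the matched cohorts are large enough would naturally turn to it, and a doubled threshold could lead them to give up the matched primary comparison without need.

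**Working it through.** **Inputs (section 8.5):** two-sided alpha 0.05, 1:1 ratio, one rate of 1.4%, difference 0.5 points. The test is not named; I assume the usual pooled-variance test of two proportions without continuity correction.

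**Formula.** With p̄ the mean of the two rates,

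n per arm = [z₀.₉₇₅·√(2p̄(1−p̄)) + z_power·√(p₁(1−p₁) + p₂(1−p₂))]² / (p₁−p₂)²

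**80% row, 1.4% against 0.9%.** p̄ = 0.0115.
- √(2 × 0.0115 × 0.9885) = 0.15078
- √(0.014 × 0.986 + 0.009 × 0.991) = 0.15074
- n = (1.95996 × 0.15078 + 0.84162 × 0.15074)² / 0.005² = 0.42240² / 0.000025, which rounds up to 7,137 per arm
- 2 × 7,137 = 14,274, the printed figure

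**80% row, 1.4% against 1.9%.** p̄ = 0.0165; the two roots are 0.18015 and 0.18012.
- n = 0.50469² / 0.000025, which rounds up to 10,189 per arm, or 20,378 in total

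**All rows:**

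| Power | Printed | Per arm, 1.4 v 0.9 | Both arms | Per arm, 1.4 v 1.9 | Both arms |
|---|---|---|---|---|---|
| 0.70 | 11,226 | 5,613 | 11,226 | 8,013 | 16,026 |
| 0.75 | 12,622 | 6,311 | 12,622 | 9,010 | 18,020 |
| 0.80 | 14,274 | 7,137 | 14,274 | 10,189 | 20,378 |
| 0.85 | 16,328 | 8,164 | 16,328 | 11,655 | 23,310 |
| 0.90 | 19,108 | 9,554 | 19,108 | 13,639 | 27,278 |
| 0.95 | 23,630 | 11,815 | 23,630 | 16,868 | 33,736 |

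All six printed values match the both-arm total for 1.4% against 0.9% exactly. Other variants do not give them as one-arm sizes. In the 80% row, a continuity correction gives 7,532 per arm, unpooled variance gives a total of 14,270, and rates centred on 1.4% (1.15% against 1.65%) give 8,667 per arm.

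**Power at given sizes.** Power = Φ{(0.005·√n − 1.95996·√(2p̄(1−p̄))) / √(p₁(1−p₁) + p₂(1−p₂))}, with n per arm.
- 14,274 per arm, 1.4 v 0.9: (0.59737 − 0.29553) / 0.15074 = 2.002, power 97.7%.
- 14,274 as a total (7,137 per arm), 1.4 v 1.9: (0.42240 − 0.35310) / 0.18012 = 0.385, power 65%.
- 30,000 per arm: above 99.9% for 1.4 v 0.9 and 99.8% for 1.4 v 1.9.
- 10,000 matched pairs (a hypothetical size): 1.4 v 0.9, (0.5 − 0.29553) / 0.15074 = 1.356, power 91%; 1.4 v 1.9, (0.5 − 0.35310) / 0.18012 = 0.816, power 79%. Read as labelled, 10,000 falls short of even the 70% row (11,226).

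**Share of the available cohort needed for 80% power:** 7,137 / 30,000 = 24%, or 10,189 / 30,000 = 34% for 1.4 v 1.9.

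**The case against.** The best reply is that the error is on the safe side. Read as labelled, the largest row (23,630) is still below 30,000. Read correctly, 95% power takes 11,815 per arm, or 16,868 for 1.4% against 1.9%. The data are retrospective, no patient is added, and no endpoint, test or estimate changes. All of this stands.

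It is also fair to say that section 8.7 does not cite Table 3 when it speaks of too few patients, and that a threshold may be set in a statistical analysis plan that is not at hand. The risk of an unnecessary change of method is therefore conditional on someone using the column that way.

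A reader might infer two stronger points, which the documents do not support:

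- **That the sufficiency conclusion fails because the label is wrong.** It does not: correcting the label lowers the requirement. The 65% figure arises only if the printed values are taken as totals and the difference also runs upward, and the protocol plans no cohort that small.
- **That dabigatran is underpowered even without attrition.** Section 6 reports an earlier 1.2-fold odds, "numerically trending greater for patients who received dabigatran", with p = 0.16. At that odds ratio, 80% power would take 31,356 per arm with apixaban at 1.4%, and more under other rate assumptions. But 30,000 is stated as a minimum, the dabigatran count is not given, and the earlier estimate was not significant and concerned bleeding-related readmissions in 2012 to 2014. Nothing obliges the sponsor to power on it.

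**Conclusion.** Table 3 is wrong as written: its figures are both-arm totals for 1.4% against 0.9%, so the per-arm requirement is overstated by a factor of 2 in every row. The identification rests on the pooled two-proportion formula, but an exact match in six of six rows leaves little doubt. Section 8.5 is also incomplete, because the table holds for only one of the two directions that its text allows; in the other, the per-arm need at 80% power is 10,189, about 43% above 7,137.

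This is an error of labelling and clarity, not an underpowered design. At the 0.5-point difference, the stated minimum of 30,000 per cohort is ample in either direction before matching. What remains open is how many pairs survive matching, and there the doubled column could mislead.

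**What to change.** In Table 3 and its copy in the abstract:

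1. Relabel the column as N total (both arms) and add a per-arm column: 5,613 / 6,311 / 7,137 / 8,164 / 9,554 / 11,815.
2. In section 8.5 and the abstract, state which cohort has the 1.4% rate and which way the 0.5-point difference runs. If apixaban is at 1.4% and the comparators at 1.9%, use per-arm values 8,013 / 9,010 / 10,189 / 11,655 / 13,639 / 16,868 and totals of twice these.
3. Tie the sufficiency sentence to its conditions: a 0.5-point difference, and at least the listed per-arm number of matched pairs in each comparison.

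The cost is wording only, with no new data and no change to the analysis. It is best done before the matched sizes are known, so that any judgement under section 8.7 on whether they suffice uses the right figure.

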### 8.6. Data management

This study will use secondary data collected in the Premier database, which is de-identified and HIPAA compliant.

### 8.7. Data analysis

Means  $\pm$  standard deviations, and medians will be provided for continuous variables. Numbers and percentages will be provided for dichotomous and polychotomous variables. Bivariate comparisons of baseline patient and hospital characteristics and readmission measurements will be provided, with appropriate tests (e.g., ANOVA test, chi-square test) used based on the distribution of the measure. A propensity score matching (PSM) 1:1 technique will be used to control for confounders when comparing each of the OAC cohorts vs. the apixaban cohort. A logistic regression analysis will be carried out on the matched patient cohorts to further evaluate the potential impact of treatment with the different OACs vs. treatment with apixaban on 1-month MB-related and all-cause readmissions. Only the index drug will be the covariate, since other patient characteristics are expected to be similar already after the PSM. Since the patient sample size attribution in the PSM process is not known, if the population sizes are not sufficient after the PSM attrition, a multivariable logistic regression analysis will be carried out to assess the potential impact of treatment with the different OACs compared to treatment with apixaban on 1-month MB-related and all-

cause readmissions, separately. The independent covariates in the regression analyses will include key patient demographics and hospital characteristics. The final list of such covariates will be determined with inputs from the Pfizer team. Additionally, we will carry out a two-part model analysis and a generalized linear model with log transformation and gamma distribution to examine the impact of treatment with the 3 different OACs vs. apixaban on MB-related and all-cause hospital readmission costs. Measurements related to exploratory objectives will be analyzed using descriptive statistics. All data analysis will be executed using statistical software SAS version 9.4.

Detailed methodology for summary and statistical analyses of data collected in this study will be documented in a Statistical Analysis Plan (SAP), which will be dated, filed and maintained by the sponsor. The SAP may modify the plans outlined in the protocol; any major modifications of primary endpoint definitions or their analyses would be reflected in a protocol amendment.

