**Variables:** Demographic, patient clinical characteristics, hospital characteristics, and key anticoagulant treatment-related information will be measured during the index hospitalization of NVAF patients. Other clinical characteristics (e.g. prior bleeding) of NVAF patients will be measured during a 12-month baseline period. The proportions of patients treated with apixaban, dabigatran, rivaroxaban, and warfarin that have MB-related, all-cause, and stroke-related readmissions that occur within 1 month of discharge of their initial hospitalization for NVAF will be evaluated. Hospital LOS and associated costs of MB-related and all-cause readmissions will be determined and compared between the other OAC cohorts and the apixaban cohort. Hospital cost data from the Premier database will reflect the hospital perspective (cost occurred to hospitals). Hospital LOS and associated costs of stroke-related readmissions will be evaluated by descriptive statistics as an exploratory analysis. Readmission rates, hospital LOS and costs associated with all-cause, MB-related and stroke-related readmissions occurring within 3 months of initial hospitalizations of hospitalized NVAF of patients will be evaluated by descriptive statistics as an exploratory analysis.

**Data sources:** The study will be conducted using the Premier Hospital database which is a nationally representative inpatient hospitalization records database that captures more than 45 million hospital discharges from greater than 600 acute care hospitals, representing approximately 20% of all hospital admissions in the U.S.

**Study size:** The preliminary data evaluation of the Premier database indicated that there are at least 30,000 patients for each of OAC cohort during the study period described for this study. With a two-sided test, an alpha-level of 0.05, and a 1:1 ratio of the comparison cohorts, and the assumed one-month MB-related readmission rate of 1.4%, and the assumed MB-related readmission rate difference of 0.5% between cohorts treated with other OACs vs. apixaban, we have estimated the following power calculation.

Power Calculation		
Nominal Power	Actual Power	N Total-One Arm
0.7	0.7	11,226
0.75	0.75	12,622
0.8	0.8	14,274
0.85	0.85	16,328
0.9	0.9	19,108
0.95	0.95	23,630

Thus, the study is expected to have sufficient sample sizes for the study measurements.

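### The matched logistic model is fixed to the index drug alone on expected balance, and adjustment is triggered only by a small sample, so imbalance left by matching goes unadjusted

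*Protocol*

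**What the plan says.** Section 8.7 gives the method of confounding control: "A propensity score matching (PSM) 1:1 technique will be used to control for confounders", applied to each comparator against apixaban. A logistic regression follows on the matched cohorts for 1-month MB-related and all-cause readmission. Its covariates are settled in one sentence: "Only the index drug will be the covariate, since other patient characteristics are expected to be similar already after the PSM". The abstract repeats it.

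One departure is allowed: "if the population sizes are not sufficient after the PSM attrition, a multivariable logistic regression analysis will be carried out".

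Baseline tables are planned: "Bivariate comparisons of baseline patient and hospital characteristics and readmission measurements will be provided, with appropriate tests". The section does not say whether these are made before or after matching, and it does not connect them to the choice of model.

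The abstract, under Data sources, says that the database "captures more than 45 million hospital discharges from greater than 600 acute care hospitals". Section 8.7 names no variance estimator and does not mention hospital clustering or matched pairs. It defers detail: "Detailed methodology for summary and statistical analyses of data collected in this study will be documented in a Statistical Analysis Plan (SAP"). It adds that major changes to the primary endpoint analysis would need a protocol amendment.

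**The concern.** This is a stated rule, not a detail left open. It has two faults.

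- **Expectation in place of a check.** The covariate list is justified by a result that matching has yet to deliver. No step follows if matching does not deliver it.
- **The wrong trigger.** Adjustment depends on sample size, but the reason to adjust is imbalance. Under the written rule, a small, well-balanced matched sample would get the multivariable model, while a large, poorly balanced one would not.

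Sample size makes the second fault matter. Section 8.5 expects at least 30,000 patients per cohort before matching. With numbers like these a standard error is small enough for a modest bias to move a test, above all for a common outcome such as all-cause readmission.

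**Working it through.** **1. The plan's own figure.** Inputs from section 8.5: "With a two-sided test, an alpha-level of 0.05, and a 1:1 ratio of the comparison cohorts", an MB readmission rate of 1.4% and a difference of 0.5 points. Taking p1 = 0.014, p2 = 0.009 and mean p = 0.0115:

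n per arm = [1.96·√(2p(1−p)) + z_power·√(p1(1−p1) + p2(1−p2))]² / (p1−p2)²

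This gives 5,613 / 6,311 / 7,137 / 8,164 / 9,554 / 11,815 for power 0.70 to 0.95. Doubled, these are 11,226 / 12,622 / 14,274 / 16,328 / 19,108 / 23,630, which match Table 3 exactly. The table therefore shows totals over both arms, although its column heading is ambiguous. 80% power needs 7,137 per arm. The formula assumes independent patients and has no design effect.

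**2. Bias from residual imbalance.** Assumptions, not in the protocol: one binary confounder with 20% prevalence in one arm, standard deviation √(0.2 × 0.8) = 0.4, and risk ratio R for the outcome. A standardised difference d puts the other arm's prevalence at 0.2 + 0.4d, that is 0.22 at d = 0.05 and 0.24 at d = 0.10. With no true drug effect, the apparent risk ratio is [1 + p1(R−1)] / [1 + 0.2(R−1)], where p1 is now that prevalence:

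- R = 1.5: 1.11/1.10 = 1.009; 1.12/1.10 = 1.018
- R = 2: 1.22/1.20 = 1.017; 1.24/1.20 = 1.033
- R = 3: 1.44/1.40 = 1.029; 1.48/1.40 = 1.057

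**3. Effect on a nominal 5% test.** Let q0 be the outcome rate, q1 = q0 × bias, SE = √{[q0(1−q0) + q1(1−q1)]/n} and shift = (q1−q0)/SE. The false-positive rate is Φ(−1.96 + shift) + Φ(−1.96 − shift). The MB rate of 1.4% is from section 8.5. The all-cause rate of 18% is the 1-month figure cited in section 6.

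Worked case, all-cause, R = 2, d = 0.10, n = 30,000: q1 = 0.186, SE = 0.00316, shift = 0.006/0.00316 = 1.90, false-positive rate about 48%.

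| Outcome, n per arm | R = 1.5, d = 0.05 / 0.10 | R = 2, d = 0.05 / 0.10 | R = 3, d = 0.05 / 0.10 |
|---|---|---|---|
| MB 1.4%, 30,000 | 5.2% / 5.8% | 5.7% / 7.7% | 7.0% / 13.0% |
| MB 1.4%, 7,137 | 5.1% / 5.2% | 5.2% / 5.6% | 5.5% / 6.9% |
| All-cause 18%, 30,000 | 8.2% / 18.0% | 15.9% / 47.6% | 37.1% / 90.0% |
| All-cause 18%, 7,137 | 5.7% / 8.0% | 7.5% / 15.3% | 12.5% / 35.3% |

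The 30,000 rows are the case with no loss in matching.

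**4. Clustering, as a range only.** Design effect for the drug contrast = 1 + (m−1) × ICC_outcome × ICC_drug. Taking 600 equal hospitals, m = 60,000/600 = 100 at 30,000 per arm. The protocol gives neither ICC. I assume 0.001 to 0.02 for the outcome and 0.05 to 0.2 for drug choice.

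- Low: 1 + 99 × 0.001 × 0.05 = 1.005; SE factor 1.002; type I error 5.1%.
- High: 1 + 99 × 0.02 × 0.2 = 1.396; SE factor 1.18; type I error 9.7%.
- At 7,137 per arm, m = 14,274/600 = 23.8; design effect 1.001 to 1.09; type I error 5.0% to 6.1%.
- Drug choice not clustered (ICC_drug = 0): design effect 1, no inflation.
- Each hospital using a single drug (ICC_drug = 1, outcome ICC 0.02, m = 100): design effect 2.98; type I error 25.6%.

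**The case against.** **Balance is a matter for the SAP.** Balance measures and thresholds are ordinary SAP content, baseline comparisons are planned, and large cohorts may match well. Much of this stands: no imbalance can be shown in advance, and the missing threshold alone would not be a finding. But the protocol does more than stay silent. It fixes the covariate list and fixes the trigger for departing from it. A SAP that added covariates because of imbalance would contradict an explicit protocol sentence about the primary analysis.

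**The primary endpoint is hardly touched.** This largely stands. At 30,000 per arm and 1.4%, the standard error of the log odds ratio is about 0.07, so significance needs an odds ratio of about 1.15. A bias of 1.8% to 5.7% from one confounder at d = 0.10 is well below that. The concern rests mainly on the all-cause contrasts, which are secondary.

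**Clustering.** A reader might infer that the plan treats patients as independent, so that its standard errors are wrong and its tests invalid at 0.05. The protocol does not support this. Limiting the covariates to the index drug does not exclude GEE, cluster-robust or conditional estimation. Only the Table 3 calculation visibly assumes independence. No ICC is given, and ignoring positive within-pair correlation would err in the conservative direction. Hospital region, urban or rural status, teaching status and bed size are listed in Table 1 as potential confounders, so the propensity score may absorb part of the hospital variation. That readmissions are seen only at the database hospitals (section 8.9) concerns outcome capture, and the protocol already lists it as a limitation.

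**Conclusion.** The point holds for covariate adjustment. As written, section 8.7 leaves any post-match imbalance in the odds ratio unless the sample also happens to be too small.

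For one assumed confounder (20% prevalence, risk ratio 2, d = 0.05 to 0.10), the false-positive rate is about 6% to 8% for MB readmission at 30,000 per arm, which is small. For all-cause readmission it is about 16% to 48% at 30,000 per arm and 8% to 15% at 7,137, which is material. A weaker or stronger confounder moves these figures widely, and if matching balances the covariates the effect is nil.

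On clustering, the supportable statement is only that the protocol makes no stated provision for it, with data from "greater than 600 acute care hospitals". Neither the size nor the direction of any error in the standard errors can be established from the document. This is a cheap improvement, not a defect that invalidates the design.

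**What to change.** Replace the index-drug-only sentence in section 8.7 and in the abstract with: *Balance will be assessed after matching by absolute standardised differences; the logistic model will include index drug plus any propensity-score covariate with a standardised difference above 0.1, whatever the matched sample size.*

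Treat 0.1 as a conventional minimum. The table shows that differences at or below it can still matter for all-cause readmission, so a fully adjusted model is a sensible sensitivity analysis for that outcome.

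State also that the logistic and cost models will use hospital-clustered robust variance, or GEE with hospital as the cluster, and confirm in the SAP how matched pairs are handled.

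The cost is a few lines of SAS, no new data, and possibly slightly wider intervals. The change should be made before outcome results are seen.
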